EDC	electronic data capture
eGFR	estimated glomerular filtration rate
EOS	end of study

EOT	end of treatment
ET	early termination
FDA	Food and Drug Administration
FOCP	female of childbearing potential
GC	glucocorticoid
GCP	Good Clinical Practice
GGT	gamma-glutamyl transferase
GI	gastrointestinal
GnRH	gonadotropin hormone-releasing hormone
HC	hydrocortisone
HIV	human immunodeficiency virus
HPA	hypothalamic-pituitary-adrenal
IB	Investigator's Brochure
ICF	informed consent form
ICH	International Council for Harmonisation of Technical Requirements for Pharmaceuticals for Human Use
INR	international normalized ratio
IRB	Institutional Review Board
IUD	intrauterine device
IUS	intrauterine system
MedDRA	Medical Dictionary for Regulatory Activities
MM	Medical Monitor
OTC	over-the-counter
PBPK	physiologically-based pharmacokinetic
PD	pharmacodynamic(s)
PK	pharmacokinetic(s)
PROMIS	Patient Reported Outcomes Measurement Information System
QD	once daily
QTcF	Fridericia-corrected QT interval
SAE	serious adverse event
SAP	Statistical Analysis Plan
SUSAR	suspected unexpected serious adverse reaction
SWYC	Survey of Well-being of Young Children
TART	testicular adrenal rest tumor
TEAE	treatment-emergent adverse event
ULN	upper limit of normal

1. INTRODUCTION

1.1. Background

1.1.1. Congenital Adrenal Hyperplasia

Congenital adrenal hyperplasia (CAH) is a serious, chronically debilitating, and life-threatening genetic disorder characterized by impaired adrenal synthesis of cortisol and consequent overproduction of adrenal androgens ([Merke and Bornstein 2005](#)).

Approximately 95% of patients with CAH have a mutation in the cytochrome P450 21A2 (CYP21A2) gene, which encodes the cytochrome P450c21 enzyme, commonly known as 21-hydroxylase ([Anderson 2010, Speiser 2018](#)).

Mutations in other genes that encode enzymes critical in adrenal steroidogenesis (CYP191, HSD3B2, CYP11B1, and POR) contribute to the remaining approximately 5% of CAH cases ([Turcu and Auchus 2015](#)). 21-Hydroxylase catalyzes the conversion of progesterone to 11-deoxycorticosterone (a precursor to aldosterone) and the conversion of 17-hydroxyprogesterone (17-OHP) to 11-deoxycortisol (the precursor to cortisol) ([White and Speiser 2000, Bachelot 2008, Doleschall 2014, Auchus 2015](#)). A 21-hydroxylase deficiency (21-OHD) thus results in a critical blockade in the adrenal steroid synthesis pathways that produce cortisol (and aldosterone in some individuals) and an accumulation of the precursors to these steroids. These steroid precursors are then diverted into the synthetic pathway for adrenal androgens, resulting in overproduction of androstenedione (A4) and downstream adrenal androgens.

Cortisol deficiency disrupts the balance of the hypothalamic-pituitary-adrenal (HPA) axis by removing the negative feedback to the hypothalamus and pituitary provided by physiologic cortisol levels. This leads to the compensatory hypersecretion of corticotropin-releasing factor (CRF) by the hypothalamus, overproduction of adrenocorticotrophic hormone (ACTH) by the pituitary gland, and consequent adrenal hyperplasia and overproduction of downstream adrenal pre-cursors and hormones such as 17-OHP and A4, leading to androgen excess ([Merke and Bornstein 2005, Speiser 2018](#)).

The clinical manifestations of CAH are the direct result of cortisol and aldosterone deficiencies and of androgen overproduction ([Merke and Bornstein 2005, Anderson 2010, Reisch 2019](#)).

Cortisol deficiency can result in adrenal insufficiency and life-threatening adrenal crises. Androgen excess may result in atypical genitalia in 46,XX newborns, risk for life threatening adrenal crisis, ongoing virilization throughout childhood, menstrual dysfunction, early puberty, testicular adrenal rest tumors (TARTs) in males, skeletal maturation leading to compromised adult height, and impaired fertility ([Merke and Auchus 2020](#)).

CAH is typically classified as either classic (the more severe form that usually presents with adrenal crisis in infancy or virilization during early childhood) or nonclassic (the milder form that may not become evident until later childhood or early adulthood). Classic CAH can be further sub-classified as salt-wasting or simple virilizing. Approximately 75% of patients with classic CAH have the salt-wasting form of CAH characterized by the loss of large amounts of sodium via urine, hyponatremia, hyperkalemia, and elevated plasma renin activity indicating hypovolemia, leading to dehydration and hypotension that can be life threatening in early infancy ([Speiser 2018](#)). Salt-wasting CAH is caused by severe aldosterone deficiency resulting from mutations that completely ablate 21-hydroxylase activity. Milder mutations that result in even 1% to 2% residual 21-hydroxylase activity enable sufficient aldosterone production to avoid neonatal adrenal crisis and produce the simple virilizing form of CAH (caused by impaired cortisol production) in the remaining 25% of classic CAH.

Refer to the Investigator's Brochure (IB) for additional information on CAH.

1.1.2. Current Treatment for CAH

There are no approved therapies for CAH. The current standard of care for CAH includes multiple daily doses of oral glucocorticoids (GCs) to replace deficient cortisol. However, as opposed to patients with other forms of adrenal insufficiency, CAH patients require supraphysiologic doses of GCs to normalize ACTH and therefore control androgen levels ([Claahsen-van der Grinten 2022](#)). This therapy is problematic as it has significant side effects (e.g., loss of bone mineral density, iatrogenic Cushing's syndrome, poor quality of life, metabolic disorders, and increased cardiovascular risk), a narrow therapeutic window, and overall poor treatment effectiveness, with higher GC doses conferring increased risk ([Steward 2019](#)). Evidence-based treatment guidelines for CAH are only beginning to be developed ([Reisch 2015, Speiser 2018](#)), and current overall treatment effectiveness for patients with CAH is poor ([Mnif 2012, Bachelot 2015](#)).

Treatment of children with CAH involves a challenging balance between GC and androgen levels. Elevated androgen levels can cause premature adrenarche and central precocious puberty as well as skeletal maturation leading to compromised adult height. GCs increase metabolic and infection risks and suppress growth by blunting the response to growth hormone ([Allen 1998](#)).

Despite the availability of GCs as a treatment for CAH, approximately two-thirds of patients with CAH are considered outside the acceptable bounds of biochemical control based on 17-OHP and A4 levels ([Han 2014](#)). Among patients with 21-OHD treated with GCs, normal serum A4 has been shown to be achieved in only 36% of patients ([Anderson 2010](#)).

Over a lifetime, the treatment of patients with CAH shifts from an emphasis on normal childhood growth to pubertal development to adult fertility and long-term health concerns, including metabolic abnormalities, cardiovascular disease, osteoporosis, and overall diminished quality of life ([Anderson 2010, Auchus 2015](#)).

Given the serious nature of CAH and the limitations and risks of chronic GC therapy, new treatments are urgently needed for patients with CAH. Corticotropin-releasing factor type-1 (CRF₁) receptor antagonism may provide a means of decoupling the treatment goals of CAH – physiologic cortisol replacement and androgen control. The ability to control androgen levels through ACTH modulation could reduce patients' dependence on high-dose GCs and alleviate the challenges associated with hyperandrogenemia and supraphysiologic GC exposure.

1.1.3. Overview of Tildacerfont

Tildacerfont, a potent and highly selective small-molecule antagonist of CRF₁ receptors, is being studied for the treatment of CAH on the basis of its ability to block the CRF₁ receptors in the pituitary gland. This blockage may decrease the CRF signal produced by the hypothalamus, thereby decreasing ACTH overproduction by the pituitary and reducing excess accumulation of downstream adrenal hormones. This mechanism of action has been validated in CAH in earlier-phase clinical studies of tildacerfont. Given its mechanism of action, tildacerfont may enable a CAH patient to have normal androgen levels while taking GC at approximately physiologic replacement levels.

Tildacerfont has been tested in 6 completed Phase 1 studies using single doses ranging from 2 to 800 mg or multiple doses ranging from 50 to 200 mg QD. Once daily dosing has been studied in 2 completed Phase 2 studies using multiple doses ranging from 200 to 1000 mg QD for 2 weeks, and up to 400 mg QD for 12 weeks. Twice daily (BID) dosing of tildacerfont has been well tolerated in adults with CAH in previous clinical studies at doses up to 200 mg BID for 2 weeks. Safety data show that tildacerfont has been generally well tolerated in all clinical studies to date, with no related serious adverse events (SAEs) in current on-going studies.

Data from the 2 completed Phase 2 studies in adults demonstrated proof of concept for tildacerfont as a treatment for CAH, with meaningful reductions in ACTH (demonstrating target engagement) and 17-OHP and A4 (demonstrating efficacy in decreasing downstream adrenal hormones in CAH) and showed continued improvement in biomarker levels over a period of 12 weeks.

Tildacerfont's mechanism of action is well-suited to potentially address the underlying pathophysiology driving excess adrenal androgen production in CAH as it blocks CRF₁ receptor engagement at the level of the anterior pituitary, and as demonstrated in completed clinical studies in adults, reduces the levels of not only ACTH, but also downstream resultant adrenal androgens and androgen precursors (17-OHP and A4) in patients with CAH. Thus, tildacerfont has the potential to effect normalization of androgen levels while allowing for GC replacement at approximately physiologic dose levels.

Nonclinical studies and clinical studies of tildacerfont are summarized in [Section 1.3](#) and full details are available in the IB.

1.2. Study Rationale

1.2.1. Rationale for the Study Design

SPR001-205 is an open-label dose ranging phase 2 study to evaluate the potential of tildacerfont to reduce androgen levels and GC burden in participants ages 2-years and older with classic CAH. SPR001-205 will be the first study of tildacerfont in children and will be used to assess safety and to determine the consistency of preliminary tildacerfont pharmacokinetics (PK) in pediatrics with those simulated in a physiologically based pharmacokinetic (PBPK) model. In Cohorts 1-3, the study will also characterize changes in androgen levels over 12 weeks of treatment, and the ability to reduce GC doses based on A4 normalization. In Cohorts 4-9, it will characterize changes in androgen levels over the first 4 weeks of treatment with BID dosing. An optional extension period will provide additional treatment with tildacerfont to provide long-term safety data for up to two years.

In completed Phase 2 studies in adult participants with classic CAH, tildacerfont exhibited an acceptable safety profile and proof-of-concept efficacy in reducing ACTH, 17-OHP, and A4 levels at effective doses, which support the continued clinical development of tildacerfont for the treatment of CAH.

As the first study of tildacerfont in a pediatric CAH population, the primary objective is to gain knowledge of the safety profile of tildacerfont. Secondary objectives of the study are to characterize the efficacy of tildacerfont in reducing A4 levels after 4 weeks of treatment (all cohorts) and reducing GC doses based on A4 normalization over 12 weeks of treatment (Cohorts 1-3), as well as comparing plasma concentrations of tildacerfont in pediatric participants with those of a simulated PBPK model.

Exploratory objectives include assessing changes from baseline in levels of ACTH, 17-OHP, A4, testosterone, and 11-ketotestosterone (11KT).

In the interest of progressing cautiously, the study's cohorts are defined by decreasing age in addition to ascending tildacerfont dose. Dosing will begin in Cohort 1 with participants in the older age group of 11 to 17 years and with the lowest dose level. Subsequent cohorts will be initiated only after a recommendation from the Data Monitoring Committee (DMC) is reviewed by the Sponsor. The final decision to progress cohorts will be made by the Sponsor. Cohort 2 will continue with participants in the older pediatric age group but dosing at a higher level (no greater than the weight-adjusted adult equivalent of 200 mg once daily [QD]). Cohort 3 will dose no higher than Cohort 2 but enroll participants in the younger age group of 2 to 10 years. An optional interim dose cohort (Cohort 1a) may be enrolled only if needed per DMC recommendation and Sponsor decision, in the event of a safety concern in participants in Cohort 1 ([Figure 1](#)).

Due to changing HPA axis dynamics across developmental stages (associated with changing GC requirements) and the fact that younger children have increased liver CYP enzyme activity (which may lead to increased tildacerfont clearance), alternative dosing regimens will also be explored, including BID dosing in Cohorts 4-9. Cohorts 4 and 5 will include adult patients (to further establish safety), Cohorts 6, 8 will include children 11-17 years of age, and Cohort 7 and 9 will include children 2-10 years of age. All cohorts including doses above 200 mg QD will be adaptive, so that the determination to initiate a cohort, and at what dose, may be determined by the Sponsor, within the guidelines of the protocol, based on recommendations by the DMC and emerging safety and exposure data ([Figure 2](#)).

Cohort 4 (adults) and Cohort 6 (11-17 years) will initiate concurrently at doses of 200mg BID. Initiation of 200mg adult equivalent BID in adolescents is supported by the prior study of 200mg QD in Cohort 2 and the prior study of doses up to 200mg BID and 1000mg QD in adults (SPR001-201).

Following DMC recommendation, Cohorts 5 and 7 may be initiated concurrently. Cohort 5 will include adults receiving either 300 or 400mg BID, and Cohort 7 will consist of children 2-10 years old receiving 200mg adult equivalent BID. If 300m BID is pursued in Cohort 5, a DMC meeting may be called to review safety data of 5 participants and make a recommendation regarding the potential enrollment of another 5 participants at a dose of 400mg.

Cohorts 8 and 9 may be initiated to investigate either a 300 or 400 mg adult equivalent BID dose (depending on DMC recommendation and Sponsor decision) in children (2-10 and 11-17 years respectively). If Cohort 8 is initiated, the DMC will convene once safety data is available for 4 participants and make a recommendation regarding initiation of Cohort 9. If 300mg equivalent BID is pursued in either cohort and escalation to 400mg is considered, a DMC meeting will be called to review safety data of 5 participants and make a recommendation regarding the potential enrollment of another 5 participants at a dose of 400mg equivalent BID. Thus Cohorts 8 and 9 may enroll up to 10 participants for each cohort ([Table 1](#)).

1.2.2. Study Population

The study is expected to enroll approximately 20 children across Cohorts 1, 2, and 3, specifically 10 participants in the 11- to 17-year-old age group (i.e., 5 participants in Cohort 1 and 2) and 10 in the 2- to 10-year-old age group (i.e., 10 participants in Cohort 3). If the optional Cohort 1a is initiated, Cohorts 1-3 may, however, enroll up to approximately 25 children.

This study will also enroll approximately 5 adults aged ≥ 18 years in Cohort 4 and 5-10 adults in Cohort 5. Therefore, up to approximately 15 adults may be enrolled. Cohorts 6 and 7 will enroll approximately 5 children each in the 11-17- and 2-10-year age groups, respectively. If Cohorts 8 and 9 are initiated, each will also enroll approximately 5-10 children. Therefore, up to 30 children may be enrolled in the BID dosing cohorts ([Table 1](#)).

1.2.3. Rationale for the Study Drug Dosing

Tildacerfont has been tested in 6 completed Phase 1 studies using single doses ranging from 2 to 800 mg or multiple doses ranging from 50 to 200 mg QD. Once daily dosing has been studied in 2 completed Phase 2 studies using multiple doses ranging from 200 to 1000 mg QD for 2 weeks, and up to 400 mg QD for 12 weeks. BID dosing of tildacerfont has been well tolerated in adults with CAH in previous clinical studies at doses up to 200 mg BID for 2 weeks. Safety data show that tildacerfont has been well tolerated in all clinical studies to date, with no related serious adverse events (SAEs) in any of the completed or the on-going SPR001-205 study. One SUSAR that included worsening diarrhea and enteritis in the context of acute adrenal insufficiency and a history of colitis was reported in SPR001-203, one of two ongoing placebo-controlled trials in adults with CAH.

As there is a food effect with tildacerfont, clinical development has been and continues to be conducted in the fed state. The clinical efficacy/pharmacodynamic (PD) data show CRF₁ receptor target engagement (reductions in ACTH) and reductions in key adrenal pre-cursors and hormones (17-OHP and A4) in participants with CAH dosed for 2 weeks with tildacerfont at 200 mg/day or higher. A 1-compartment PK model with first-order absorption and elimination was fit to PK data from Study SPR001-201 and used to estimate the steady-state exposure for each participant at each dose.

The adult exposure levels observed after 2 weeks of treatment were extrapolated to pediatric participants based on body weight and age for this study using a PBPK approach based on healthy adults. The PBPK model was based on *in vitro* and *in vivo* information on the metabolism and PK of tildacerfont and was validated using the plasma concentration-time profiles in healthy adults in the fed state. To account for differing CYP3A4 expression by age, the Upreti ontogeny profile was used in the pediatric dose predictions in three age groups, 2 to 5, 6 to 10, and 11 to 17 ([Upreti and Walhstrom 2016](#)). Pediatric doses on a mg/kg basis were predicted by age group to correspond to the adult exposures at the same dose levels. Within the lower dose cohorts (50 mg and 100 mg), dose bands were constructed such that participants would not receive a dose greater than 20% over the predicted mg/kg conversion. Weight bands were constructed such that participants in higher dose cohorts would not receive a dose greater than 10% over the predicted mg/kg conversion of the corresponding adult dose.

Preliminary PK data from Cohorts 1-3 show that the PBPK model overestimates drug exposure in children, such that the weight-based adult equivalent doses utilized in the children do not provide the exposures observed in adults. Additionally, an inverse relationship between age and exposure is apparent. This may be due to differences in drug metabolism across developmental stages, specifically CYP enzyme activity which is the primary driver of tildacerfont elimination. CYP enzyme activity peaks in early childhood and declines into adulthood. Consequently, children sometimes require relatively higher doses than adults to achieve optimal exposures of drugs that are eliminated by CYP-dependent metabolism (i.e., the Upreti ontogeny profile may not have adequately adjusted for physiologic differences that impact tildacerfont exposure).

Higher doses and more frequent administration of tildacerfont may support increased and more consistent exposure in spite of the more rapid elimination in children. Further dose exploration is supported by the fact that no safety signal has been observed in Cohorts 1-3 at the time of this amendment, which includes 30 pediatric participants on doses up to 200mg adult equivalent QD for up to 24 weeks (1Nov23). Additionally, the 200mg QD dose which is the dose being used in the on-going adult CAH studies have a safety margin of 13.7 relative to the NOAEL from pre-clinical studies. This margin is expected to be greater in children because the exposures observed in SPR001-205 have been substantially lower than those observed in the adult studies.

The maximum planned dose is 400 mg BID, subject to adjustment based on safety and PK data obtained during this study. The design of this amendment allows for the evaluation of exposure in adults starting at 200mg BID and continuing (per DMC recommendation) with dosing up to 400mg BID, such that all new dosing regimens have been or will be tested in adults prior to children. Additionally, pediatric exposure at 200mg BID can be evaluated prior to increasing to up to 400mg BID in children. Given that pediatric exposures are observed to be less in children than adults, this stepwise approach optimizes the ability to ensure that no pediatric exposures exceed those previously studied in adults.

Pediatric weight-based tildacerfont dose levels equivalent to doses of 50 mg, 100 mg, 200 mg QD, as well as 200mg, 300 mg, and 400 mg BID in adults are defined in [Table 2](#) by age group.

1.3. Risk/Benefit Assessment

Tildacerfont has been generally well tolerated at effective doses and has demonstrated the ability to reduce ACTH and downstream adrenal androgen production in adult patients with CAH and elevated adrenal androgen levels in Phase 2a studies. The most frequently reported non-procedural associated adverse events (AEs) were headache and diarrhea. No drug-related SAEs have been reported in completed clinical studies to date.

Potential clinically significant risks identified in the pre-clinical program include histopathological changes in the thyroid gland and male reproductive tract, developmental toxicity and mild, possibly treatment-related trends in increased Fridericia-corrected QT interval (QTcF) duration. However, no corresponding functional decline in thyroid or male reproductive biochemical assessments has been observed in human studies completed to date, nor have any cardiovascular safety concerns been noted with either vital signs or electrocardiogram (ECG) monitoring. Developmental toxicity has not been evaluated in human clinical trials.

Hepatic effects were also noted in the pre-clinical program, and reversible liver enzyme elevations have been observed in clinical studies.

Additional details of known and potential risks of tildacerfont are provided in the IB. Study SPR001-205 has incorporated multiple design elements to mitigate these potential risks including extensive laboratory assessments ([Section 7.1.5](#)), an independent Hepatic Adjudication Committee to assess potential liver issues, ECG monitoring ([Section 7.1.4](#)), contraception requirements ([Section 4.2.3](#)), and stopping criteria ([Section 6.1](#)).

As tildacerfont is metabolized by CYP3A4, drug-drug interaction risk necessitates the prohibition of concomitant use of known moderate to strong inducers or inhibitors of CYP3A4. Moreover, as tildacerfont is a moderate inhibitor of CYP3A4, drugs that are sensitive substrates or narrow-therapeutic-range substrates of CYP3A4 and/or breast cancer resistance protein (BCRP) must be avoided; for sensitive substrates or narrow-therapeutic-range substrates of BCRP in the absence of CYP3A4, cautionary use is advised with separation of at least 10 hours from tildacerfont and ongoing assessment for loss of efficacy.

2. OBJECTIVES AND ENDPOINTS

COHORTS 1-3 (12-week Treatment)	
Objectives	Endpoints
Primary	
To evaluate the safety of tildacerfont in participants with CAH	AEs and SAEs
Secondary	
To determine the efficacy of tildacerfont on disease control or reduction of GC use in participants with classic CAH during 12 weeks of treatment	Proportion of participants who achieve a reduction in A4 or reduction in GC dosing during treatment period
To determine the efficacy of tildacerfont on disease control in participants with classic CAH after 4 or 12 weeks of treatment	Proportion of participants with elevated baseline A4 who achieve a reduction in A4 at Week 4
	Proportion of participants with elevated baseline A4 who achieve A4 normalization at Week 4 or Week 12
To determine the consistency of preliminary tildacerfont PK in participants with those simulated in a PBPK model	Tildacerfont plasma concentrations will be compared with the current PBPK simulation for consistency
Exploratory	
To explore changes in pharmacodynamic (PD) biomarkers in participants with CAH	Change from baseline in adrenocorticotrophic hormone (ACTH), 17hydroxyprogesterone (17-OHP), A4, testosterone, and 11-ketotestosterone (11KT)
COHORTS 4, 5, 6, 8, 7, and 9 (4-week Treatment)	
Objectives	Endpoints
Primary	
To evaluate the safety of tildacerfont in participants with CAH	Adverse events (AEs) and serious adverse events (SAEs)

Secondary	
To determine the efficacy of tildacerfont on disease control in participants with classic CAH after 4 weeks of treatment	Proportion of participants who achieve reduction in androstenedione (A4) at Week 4
	Proportion of patients who achieve A4 normalization at Week 4.
To determine the consistency of preliminary tildacerfont pharmacokinetics (PK) in participants with those simulated in a physiologically based PK (PBPK) model	Tildacerfont plasma concentrations will be compared with the current PBPK simulation for consistency
Exploratory	
To explore changes in pharmacodynamic (PD) biomarkers in participants with CAH	Change from baseline in adrenocorticotropic hormone (ACTH), 17hydroxyprogesterone (17-OHP), A4, testosterone, and 11-ketotestosterone (11KT)
EXTENSION (Cohorts 1-9)	
Objectives	Endpoints
Primary	
To evaluate the safety of tildacerfont in participants with CAH	AEs and SAEs
Secondary	
To determine the efficacy of tildacerfont on reduction of glucocorticoid (GC) use in participants with classic CAH after 4 weeks or 12 weeks of treatment	Proportion of participants who achieve reduction in glucocorticoid (GC) dosing (beyond 12 weeks for Cohorts 1-3 and beyond 4 weeks for Cohorts 4-9)
	Proportion of participants who achieve approximately physiologic GC dosing ($\leq 11 \text{ g/m}^2/\text{d}$)
To determine the efficacy of tildacerfont on disease control in participants with classic CAH	Proportion of participants with elevated A4 at completion of treatment period (Week 12 for Cohorts 1-3 and Week 4 for Cohorts 4-9) who achieve a reduction in A4
	Proportion of participants with elevated A4 at completion of treatment period who achieve A4 normalization

Exploratory	
To explore changes in pharmacodynamic (PD) biomarkers in pediatric participants with CAH	Change from baseline in adrenocorticotrophic hormone (ACTH), 17-hydroxyprogesterone (17-OHP), A4, testosterone, and 11-ketotestosterone (11KT), (at Week 4 for all cohorts and Week 12 for Cohorts 1-3)
To explore the impact of tildacerfont on skeletal maturation	Change from baseline in predicted adult height

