8.3.6. Pharmacodynamic Analyses

The PD Population will be used for all PD analyses.

Change from baseline in PD biomarkers, ACTH, 17-OHP, A4, testosterone, and 11KT will be summarized descriptively using the 8-point summary as well as geometric mean ratios comparing baseline to post baseline, as appropriate. T will be summarized separately for males and females.

Change from baseline in select PD ratios will also be summarized, A4/T (males only) and 11KT/T (males and females, separately). Other ratios may be identified in the statistical analysis plan.

The proportion of participants with a reduction in biomarkers at Weeks 4 (all cohorts) and 12 (Cohorts 1 to 3 only) will be summarized descriptively, including by subgroup, baseline A4 \leq ULN, Baseline A4 $>$ ULN:

- Any reduction
- \geq 50% reduction
- A4 \leq ULN

Change from baseline in GC total daily dose at Week 12 and during the extension period will be summarized descriptively:

- Absolute change (mg)
- Absolute change adjusted for body surface area (mg/m²)
- Percent change (%)
- Proportion of participants with GC reduction
- Proportion of participants with baseline dosing $>$ 3x daily who decrease frequency of administration \leq 3x daily

The proportion of participant with a \geq 1 mg/m² GC reduction or any reduction from baseline in A4 at Week 12 will be summarized descriptively.

Changes in adrenal biomarkers and GC will be summarized in a similar manner for the extension period.

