7.1	To evaluate the safety of tildacerfont in subjects with CAH	AEs and SAEs	14.1
8.	Secondary		
8.1	To determine the efficacy of tildacerfont on reduction of glucocorticoid (GC) use in subjects with classic CAH after 4 weeks or 12 weeks of treatment	

• Proportion of subjects who achieve reduction in glucocorticoid (GC) dosing (beyond 12 weeks for Cohorts 1-3 and beyond 4 weeks for Cohorts 4-9)

• Proportion of subjects who achieve approximately physiologic GC dosing (<math>\leq 11 \text{ g/m}^2/\text{d}</math>)

	13.1.1
8.2	To determine the efficacy of tildacerfont on disease control in subjects with classic CAH	

• Proportion of subjects with elevated A4 at completion of treatment period (Week 12 for Cohorts 1-3 and Week 4 for Cohorts 4-9) who achieve a reduction in A4.

• Proportion of subjects with elevated A4 at completion of treatment period who achieve A4 normalization

	13.1.2
9.	Exploratory		
9.1	To explore changes in pharmacodynamic (PD) biomarkers in pediatric subjects with CAH	Change from baseline in adrenocorticotropic hormone (ACTH), 17-hydroxyprogesterone (17-OHP), A4, testosterone, (at Week 4 for all cohorts and Week 12 for Cohorts 1-3)	13.2.1
9.2	To explore the impact of tildacerfont on skeletal maturation	Change from baseline in predicted adult height	5.3.1.4

**Table 4** Detailed Exploratory Objectives and Endpoints

Objective		Endpoint	Section Number
1. Change from baseline over 12 weeks			
1.1.	To explore changes from baseline in pharmacodynamic (PD) biomarkers in pediatric subjects with CAH over 12 weeks	Log-transformed change from baseline in ACTH	13.2.1
1.2.		Log-transformed change from baseline in 17-OHP	13.2.1
1.3.		Log-transformed change from baseline in A4	13.2.1
1.4.		Log-transformed change from baseline in T, by sex	13.2.1
2. Change from baseline in ratios over 12 weeks			
2.1.	To explore changes in select PD biomarkers ratios in pediatric subjects with CAH over 12 weeks	Change from baseline in A4/T ratio (males only)	13.2.2
3. Proportion of subjects with reduction [1] overall and [2] by subgroup (Baseline A4 ≤ ULN; Baseline A4 > ULN) [3] by subgroup (Male; Female)			

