### *13.2.4 Change from Baseline in Glucocorticoid Total Daily Dose*

The following metrics of GC reduction include change from baseline (mg in HCe), change adjusted for BSA (mg/m^2), and percent change from baseline. These measurements of change from baseline in GC total daily dose at Week 12 will be summarized by cohort and overall. A listing of GC reduction will be provided.

The proportion of subjects who achieve the following criteria will be summarized in a table with descriptive statistics by cohort and scheduled time point:

- Any GC reduction
- $\geq 1 \text{ mg/m}^2$  GC reduction or any reduction from baseline in A4 at Week 12 (secondary efficacy endpoint).

A listing of prior and concomitant GC medications will provide information about subjects whose baseline dosing  $> 3 \times$  daily decreases frequency of administration  $\leq 3 \times$  daily.

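### The cut-off for approximately physiologic glucocorticoid dosing, an extension-only secondary endpoint, is printed in g/m²/d instead of the mg-based units used for every other glucocorticoid dose

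*Protocol*

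**What the plan says.** The extension period has a secondary objective on reducing GC use. One of its endpoints in protocol Section 2 is "Proportion of participants who achieve approximately physiologic GC dosing". The threshold follows in brackets, and the printed run (with its typesetting code) is "approximately physiologic GC dosing ($\leq 11 \text{ g/m}^2/\text{d", that is, at most 11 g/m²/d. The extension block of the protocol synopsis prints the same limit. SAP Table 3, row 8.1, repeats it after "Proportion of subjects who achieve approximately physiologic GC dosing".

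Elsewhere the GC scale is in milligrams:

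- Protocol 8.3.6 lists "Absolute change adjusted for body surface area (mg/m²" as a summary of GC change, and its composite criterion is a reduction of at least "1 mg/m² GC reduction or any reduction from baseline in A4 at Week 12 will be summarized descriptively".
- SAP Table 4 (rows 4.1 and 4.2) and SAP 13.2.4 give GC change in mg and mg/m².
- SAP 9.4.17.3 takes the dose at a visit from an eCRF field recorded in mg, and SAP 12.3 summarises it in mg hydrocortisone equivalents.
- The stress-dosing table in protocol 5.3.1.3 uses mg and mg/m².

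SAP Section 15, which lists departures from the protocol's analyses, does not mention the unit. SAP Section 4 places the extension analysis in a separate SAP.

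**The concern.** The figure is the decision rule of a pre-specified responder endpoint, so its unit determines who counts as a responder. A limit 1,000 times larger than the same number in mg cannot separate participants on physiologic doses from those on supraphysiologic doses, which is the purpose of the endpoint. Neither document prints this threshold in any other unit, so a reader cannot settle the matter from another section. It is also the only number that either document attaches to physiologic GC dosing.

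**Working it through.** The plan offers no calculation to reproduce here. The check is a unit conversion, followed by a comparison with the GC doses that the documents name.

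**Inputs**

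- Printed limit: 11 g/m²/d (protocol synopsis, protocol Section 2, SAP Table 3 row 8.1).
- Largest GC amount named: for acute adrenal crisis (protocol 5.3.1.3), a hydrocortisone bolus of up to 100 mg/m², then up to 100 mg/m² per day.
- Potency relative to hydrocortisone (SAP Table 6): prednisone 4; prednisolone and methylprednisolone 5.
- Body surface area: 0.5 to 2.0 m², assumed, because the documents give no distribution.

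**Step 1. Convert the limit.** 11 g/m²/d × 1,000 mg/g = 11,000 mg/m²/d.

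**Step 2. Compare with the largest named dose.** 100 + 100 = 200 mg/m² in a day, and 11,000 / 200 = 55. Against the 100 mg/m² per day alone, 11,000 / 100 = 110. Even crisis treatment stays far below the printed limit.

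**Step 3. Find the dose needed to miss the criterion.** Divide the limit by potency:

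- prednisone: 11,000 / 4 = 2,750 mg/m²/d
- prednisolone or methylprednisolone: 11,000 / 5 = 2,200 mg/m²/d

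In absolute terms the limit allows 11,000 × 0.5 = 5,500 mg to 11,000 × 2.0 = 22,000 mg of hydrocortisone equivalents per day over the assumed body surface range.

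**Step 4. See whether the criterion can discriminate.** Take an illustrative grid of daily hydrocortisone-equivalent doses: 5, 8, 10, 11, 12, 15, 20, 25, 30 and 40 mg/m²/d. The grid is an assumption, because the documents give no dose distribution.

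| Unit attached to 11 | Grid doses meeting the limit |
|---|---|
| g/m²/d, as printed | 10 of 10 |
| mg/m²/d, the unit used elsewhere | 4 of 10 |

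The second row shows only what the unit does to the criterion. It is not a statement that 11 is the right value.

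**Step 5. Trace where the threshold is used.** SAP Table 3 points row 8.1 to SAP 13.1.1, which covers reduction in A4 or GC dose and contains no such limit. SAP Table 5 has no responder definition for this endpoint. Protocol 8.3.6 does not list it. SAP 13.2.4 concerns Week 12 change ("These measurements of change from baseline in GC total daily dose at Week 12 will be summarized by cohort and overall") and does not contain the threshold. The misprinted unit therefore stands in three places, all of them extension endpoint tables.

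**The case against.** The strongest reply is that this is a visible misprint that would not survive programming. Doses are collected in mg and summarised in mg hydrocortisone equivalents, the endpoint is labelled physiologic, and the protocol's rationale says that patients generally need supraphysiologic doses. Someone would have to convert the data to grams to produce the meaningless result, and nothing shows that an analysis has gone or will go wrong. That is fair as to likelihood. It does not make the printed rule correct, and the threshold appears nowhere else from which to confirm it.

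Several stronger readings are tempting but not supported:

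- **That the trial's efficacy conclusions are at risk.** The threshold belongs to one extension endpoint, and the analysis in the supplied SAP does not apply it.
- **That the error will pass into the extension SAP.** That document is not available. The same unit stands in the protocol and in SAP Table 3; anything beyond that is conjecture.
- **That exactly 100% of participants would be responders.** This holds only for those with a recorded GC dose. No missing-data rule is given for this endpoint, and every row of SAP Table 5 counts missing as non-response, so a participant without a dose could still count as a failure.
- **That the dose has no hydrocortisone-equivalent scale.** SAP 9.4.17.1 supplies the conversion and SAP 9.4.17.2 divides the converted dose by body surface area. What is missing is a link from the endpoint to that definition, and the text of 9.4.17.2 names only the baseline dose.

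**Conclusion.** The concern holds as a wrong unit in the decision threshold of one extension-only secondary endpoint. As printed, the limit is 11,000 mg/m²/d, 55 times the largest GC amount in either document. Every participant with a recorded dose meets it at every visit, including baseline, so the endpoint cannot show a move to physiologic dosing. The conclusion rests on the printed text and on recorded doses staying within the range that the documents describe; the body surface range and the dose grid are illustrations and do not drive it. The primary safety endpoint and the 4- and 12-week efficacy analyses are unaffected. The documents do not establish which threshold value is right, and this review does not propose one.

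**What to change.** Three linked text changes:

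1. Have the sponsor confirm both the value and the unit of the threshold. Then reconcile the protocol synopsis, protocol Section 2 and SAP Table 3 row 8.1 with the mg/m²/day scale used for GC dose elsewhere.
2. At the endpoint, add a cross-reference to the hydrocortisone-equivalent, body-surface-adjusted dose of SAP 9.4.17.1 and 9.4.17.2, and extend the wording of 9.4.17.2 so that it covers post-baseline visits.
3. Use the reconciled threshold in the extension SAP, with a responder definition that says how a missing dose is handled.

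The cost is a few lines of text. No data collection or sample size changes, and no analysis in the supplied SAP has to be altered.
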